8.1 Duration of the Study

Enrollment is expected to take place over a period of 9–12 months. Each site is expected to enroll 60 to 120 participants during this period, which restricts the number of participating CTPs to 4 with a large program census. If enrollment is slower than expected, such that 60 to 120 participants are not randomized within 12 months, the trial may be discontinued early. The total duration of study participation will be the 13 weeks of the post-discharge intervention period plus the initial, variable length of residential treatment (7–42 days). Thus, enrollment should be completed and all study data should be collected within 15–18 months.

9.0 SUBJECT SELECTION

Participants enrolling at participating residential facilities for treatment of substance abuse who meet basic inclusion/exclusion criteria should be considered for the TELE protocol. There are 60 to 120 participants required for randomization in this study at each site. It is estimated that approximately two thirds of those candidates who sign informed consent will complete the baseline data collection, meet all other eligibility criteria, and

be randomized. Some participants may not complete the treatment program and may leave without a continuing care plan in place; others may withdraw consent prior to randomization.

9.1 Eligibility Criteria

Eligible candidates in the participating residential program will be informed of the study as soon as practical, but within 7 days from their admission to the residential program (days 1–7, recommended by day 3).

Eligible candidates include men and women who are at least 18 years of age and have the ability to understand and provide written informed consent. Candidates must be voluntarily admitted (not civilly committed) to a residential program for rehabilitation treatment (not admitted for detoxification only) and must have had a diagnosis for substance abuse or dependence for a minimum of 7 days and a maximum of 42 days. Candidates should be referred by a program servicing the targeted counties on admission and should plan to return to residence in targeted counties after discharge. Candidates must be able to be contacted via phone after discharge. Candidates will be excluded from consideration for the study if they have evidence of current suicide intention or recent (<30 days prior to admission) suicide attempt.

Participants must complete all study procedures and assessments in the specified order, but flexibility in timing is permitted within the ranges provided. Participants must give informed consent to participate in the study within 7 days of residential facility admission (recommended by day 3), and all baseline measures must be completed as close as possible to the date of the admission, ideally within the first 7 business days after admission.

Randomization will occur as close as possible to the date of the participant's planned discharge, ideally within the 2 business days prior to the planned date of discharge or on the actual day of discharge. To be eligible for randomization, individuals must have completed all consent and baseline assessment measures, have been provided a continuing care plan from the residential program, and met with the research assistant.

Participants will be withdrawn from study eligibility, if, after being consented during the first 7 days of their residential treatment, they do not complete the study baseline measures as close as possible to the date of admission to the residential facility, ideally within the first 7 business days after admission, or if they leave the treatment program for any reason without completing and discussing a continuing care plan, or if they leave without being randomized.

See sections 9.1.1 and 9.1.2 for a complete list of inclusion and exclusion criteria.

Based upon estimates from the CTP staff, approximately 67.5% of those signing informed consent forms will complete the data collection and treatment planning activities (study baseline), will meet all other eligibility criteria, and will be randomized. Data on the number of participants giving consent and the number randomized will be collected for feasibility study purposes.

9.1.1 Inclusion Criteria

- 1. Men and women at least 18 years of age
- 2. Ability to understand and give written informed consent within the first 7 days of admission to the residential facility
- 3. Voluntary admission (not civilly committed) to the residential facility for rehabilitation treatment (not admitted for detoxification only)
- 4. Diagnosis of substance abuse or dependence (excluding nicotine and caffeine) according to residential facility records
- 5. Referral by a program servicing the targeted counties, with plans to return to residence in targeted counties after discharge from the residential treatment facility
- 6. Ability to be contacted via phone by research staff upon release from residential treatment

9.1.2 Exclusion Criteria

- 1. Unable or unwilling to provide informed consent
- 2. Failure to complete prescribed treatment, study baseline measures, or no provision for a continuing care plan prior to departure from the residential center
- 3. Evidence of current suicide intention or recent (\leq 30 days prior to admission) suicide attempt
- 4. Enrollment in a residential treatment program for < 7 or > 42 days

10.0 STUDY PROCEDURES (must occur in this order)

10.1 Screening and Obtaining Written Informed Consent

10.1.1 Candidates Log

In order to track the number of individuals who are invited to participate in the study, a log will be maintained by the research assistant, recording the number of candidates who received an invitation to participate in the study. Of those who were approached for participation, aggregated data will be provided to the Lead Node at the conclusion of the trial for those candidates who were excluded from study participation and thus did not sign a written consent form. These data will include the summary of the number of males and the number of females, categorization of age (e.g., how many candidates were between 20 and 29 years old), and categorization of the reasons candidates were not consented who were approached for participation.

Additional information will be collected on the Screening Form and the Randomization Form on all participants who sign the consent form. This information will record whether each consented candidate completed all study requirements to be randomized into the study. For candidates who fail to achieve randomization, the reason for this outcome will be recorded (e.g., premature discharge, failure to meet all eligibility criteria).

10.1.2 Initial Candidate Screening & Informed Consent

Each eligible candidate should be informed by the research assistant about the TELE feasibility study, as early in their residential stay as possible, following whatever plan the particular center has developed, but this must occur within the first 7 days of the candidate's admission to the program. The candidate should receive a detailed explanation of the study, with the opportunity to ask questions, and then be invited to participate in the study.

Candidates who agree to participate in TELE should be given a copy of the IRB approved consent form, with ample time to review the form. The research assistant should remain available to answer any questions the candidate might have about the study or explain any language in the consent the candidate does not understand.

Candidates who agree to participate will sign the informed consent and be given a copy of the signed agreement. At that time, or at a suitable time as close as possible to the date of the participant's admission to the residential facility, ideally within the first 7 business days after admission, the information for all baseline measures is collected by the research assistant.

10.2 Baseline Assessments

Baseline assessments must be completed as close as possible to the date of the participant's admission to the residential facility, ideally within the first 7 business days after admission to the facility following written informed consent, and will consist of completion of the following case report forms and other information gathering tools:

- 1. CTN Addiction Severity Index-Lite Version 1
- 2. HIV Risk Behavior Survey (RBS)
- 3. Screening Form
- 4. Randomization Form
- 5. Locator Form

10.3 Study Assessments Prior to Discharge

10.3.1 Pre-Discharge Interview

All participants will receive their program's routine continuing care plan (discharge plan), developed by their residential counselor or developed as usual at the specific treatment program.

All participants will meet with the research assistant prior to randomization as close as possible to the date of the participant's planned discharge, ideally within the 2 business days prior to the planned date of discharge or on the actual day of discharge. At the meeting, the research assistant will do the following:

1. Review the consent form signed by the participant to assure that the participant continues to understand and be a willing participant in the TELE study

- 2. Review the locater form previously completed by the participant and update as needed
- 3. Discuss the week-13 post-residential program follow-up visit:
 - a. Describe the visit (participant will be expected to answer questions, provide a urine sample, and perform a breath alcohol test).
 - b. Attempt to schedule the date, time, and the location of this visit. The participant should be given an appointment card (or equivalent) with the agreed-upon date for the follow-up visit.
 - c. Provide each participant with contact information for the research assistant who will conduct the follow-up visit, in case the participant needs to reschedule the week 13 visit and the locater information changes during the 13 weeks following discharge.
 - d. Obtain signed release form(s) for program(s) to which the participant is referred for post-discharge continuing care activities in order to verify compliance and release form(s) for arrest and conviction records to possibly verify self-reported criminal justice activity that occurred after discharge from the residential facility.

10.3.2 Review of the Continuing Care Plan and Randomization

All participants will meet with the TELE counselor prior to randomization as close as possible to the date of the participant's planned discharge, ideally within the 2 business days prior to the planned date of discharge or on the actual day of discharge, to review the continuing care plan. If a thorough review has been performed by the residential program counselor, the TELE counselor only needs to ensure participant comprehension of this plan. Subsequently, the TELE counselor will perform the manual randomization (of participants remaining eligible) to either telephone counseling calls (TCG) or standard of care (SCG). This will be done as close as possible to the date of the participant's planned discharge, ideally within the 2 business days prior to the planned date of discharge or on the actual day of discharge.

A set of envelopes, numbered sequentially and provided to each site prior to the recruitment of participants, will be used to determine a participant's random assignment. At the time of randomization, the TELE counselor will remove the envelope with the next sequential number. Upon opening the envelope, the TELE counselor will inform the participant of the group to which he or she is randomized. If the participant is randomized to SCG, the TELE counselor should remind the participant of his or her planned continuing care and the 13-week visit, and conclude the meeting. If the participant is randomized to the TCG, the TELE counselor should schedule the first call during this meeting. The participant should be reminded of his or her planned continuing care and the week 13 follow-up visit, and the interview should be concluded. Refer to the Counselors Manual for more details.

The goal of this pre-discharge meeting is to establish rapport with all study participants to avoid bias of the study results, which might occur if only the group randomized to follow-up phone calls had had the pre-discharge meeting.

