Randomization will be performed at each participating residential program by using a randomization sequence developed by the statistician at the Lead Node and provided in sealed, sequentially numbered envelopes to the participating centers. A stratified randomization with permuted blocks will be employed. The randomization scheme will stratify by site (residential program) in order to maintain an approximate balance between treatment groups at each site.

For the TCG participants, calls will be made during weeks 1, 2, 4, 6, 8, 10, and 12 after discharge from residential care. Telephone calls will focus on the participants' self-reported adherence to the continuing care plan that was provided to them at discharge. Contact success and duration of all calls will be documented. A portion of calls will be recorded and at least 10% of successful calls will be randomly selected and scored for fidelity to the intended call procedures.

Participants in each group will be assessed for treatment effects at a follow-up visit expected to occur at 13 weeks after discharge from the residential setting. Day of discharge will be considered as day 0 of follow-up. The window for this visit will be from days 88–116 following discharge from the residential program.

During the study, data will be reviewed by study monitors utilizing the procedures established by the CTN to assess the completeness and accuracy of data collected.

The analysis of the feasibility and efficacy data will be presented to the Steering Committee for consideration in their decision on whether to conduct a larger, multi-site trial.

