10.4 Intervention after Discharge

Following discharge, a total of 7 telephone contacts at weeks 1, 2, 4, 6, 8, 10, and 12 will be made by the TELE counselor to all participants randomly assigned to the TCG. Each contact will follow the scripted procedure outlined in the Counselors Manual. The same procedure will be followed upon each contact. Up to 3 attempts will be made to contact the participant for each of the 7 scheduled calls, regardless of the outcome of the previously scheduled call.

Unless consent to participate is expressly revoked by the individual, he or she will continue to be contacted as scheduled. Attempts to contact the participant and the outcome of the call will be recorded on the participant contact form in the CRF. The SCG participants will not be contacted by the TELE counselor following their pre-discharge session.

A portion of calls will be recorded and at least 10% of successful calls will be randomly selected and scored for fidelity to the intended call procedures. Each node supervisor will provide supervision to the TELE counselor, per standard practice for the particular program.

In order to provide standardization across all TCG calls, the TELE Counselors Manual provides directions for conducting these calls. Information obtained during the course of the call will not be used as research data with the exception of serious adverse events. These events disclosed by the participant will be documented and reported as described in section 12.0.

The manual also provides minimal instructions for handling medical emergencies such as suicidal threats. Each facility is expected to have a written plan in place for emergency situations. If a plan is not in place, a procedure will be developed by the facility and should be available for review by the node quality assurance (QA) monitor prior to enrollment. Each facility has the responsibility for training its research staff on the facility's emergency plan.

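### The counselor who makes the calls also takes the next envelope from a site-stratified blocked sequence, with no envelope tied to a participant beforehand, so envelope order could follow a partly predictable arm

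*Protocol*

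**What the plan says.** - **Review before assignment (Protocol 10.3.2).** "All participants will meet with the TELE counselor prior to randomization", to go over the continuing care plan. If the residential counselor has already reviewed it thoroughly, "the TELE counselor only needs to ensure participant comprehension of this plan". No criterion for a thorough review is given.
- **Timing (10.3.2).** Both the meeting and the randomization are to fall as near to planned discharge as possible, "ideally within the 2 business days prior to the planned date of discharge or on the actual day of discharge".
- **Envelope (10.3.2).** After the review, "the TELE counselor will remove the envelope with the next sequential number", opens it and tells the participant the group. The section does not say that an envelope is assigned to a participant before that moment.
- **Calls (10.4).** The seven calls "will be made by the TELE counselor to all participants randomly assigned to the TCG". The role that opens envelopes therefore works with assignments in the open.
- **Sequence (8.0 and 13.7).** "A stratified randomization with permuted blocks will be employed", with allocation 1:1 and site as the only stratum. Assignments are "provided in sealed, sequentially numbered envelopes to the participating centers". Section 13.7 leaves the block size to the statistical group at the Lead Node and does not disclose it.
- **Second person (11.5).** The research assistant confirms eligibility through the Randomization Form, and the assigned group is recorded on that same form. Under 10.6.1 a research assistant also conducts the week-13 visit.

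**The concern.** Sealed, numbered envelopes stop a person from reading the next assignment. They do not stop a person who has seen past assignments from inferring it, because a blocked sequence returns to balance within each site. The person placed to infer it here also has two kinds of latitude before the envelope is opened:

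1. When two participants are near discharge together, nothing in 10.3.2 settles who takes the next envelope.
2. The plan review may be a full review or only a check of comprehension.

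If either followed the expected arm, the groups could differ before the first call. The first main efficacy measure in 13.3 is self-reported engagement in the activities of the very plan being reviewed. Section 5.1 item 7 makes the effect size one of the critical outputs, for use in powering a later trial. Section 13.3.1 plans no covariate adjustment for baseline values, and an unrecorded difference in review depth could not be recovered afterwards.

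**Working it through.** **The plan's own figure.** Section 13.5 gives 60 to 120 randomized per site and 360 in total. Four sites give 4 × 60 = 240 to 4 × 120 = 480. The midpoint of 90 gives 4 × 90 = 360, or 180 per arm, so the total reproduces. The Protocol states no predictability figure.

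**Inputs.** Allocation is 1:1 in permuted blocks with site as the only stratum (8.0, 13.7). Block size is not stated, so sizes 2 to 12 are assumed. A site of 90 is used for simulation. The number of counselors per site is not stated: 10.3.2 and 10.4 use the singular, 15.1 and 15.2 the plural.

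**Formulas for a fixed block of size 2m, all earlier assignments seen.**

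- Expected correct guesses per block, guessing the arm that is behind and tossing a coin when level: m + (4^m / C(2m, m) − 1) / 2.
- Share of assignments that are certain, because one arm in the block is used up: 1 / (m + 1).

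Worked for a block of 4 (m = 2): 2 + (16/6 − 1)/2 = 2.833, and 2.833/4 = 70.8% correct; 1/3 = 33.3% certain; 360 × 1/3 = 120. Full enumeration of the blocks gives the same results.

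| Block size | Correct guesses | Certain | Certain, of 90 | Certain, of 360 |
|---|---|---|---|---|
| 2 | 75.0% | 50.0% | 45 | 180 |
| 4 | 70.8% | 33.3% | 30 | 120 |
| 6 | 68.3% | 25.0% | 22.5 | 90 |
| 8 | 66.6% | 20.0% | 18 | 72 |
| 12 | 64.3% | 14.3% | 12.9 | 51 |

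The certainty columns need the block size to be fixed and either known or inferred. Guessing does not, because completed blocks are balanced and the running balance at the site is enough.

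**Varying, undisclosed blocks** (simulation, 2,000 sites of 90, guessing whichever arm is behind at the site):

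- Sizes 4 and 6 mixed: 69.2% correct overall. The arms are unequal 61.2% of the time, and the guess is then right 81.3% of the time. Check: 0.612 × 0.813 + 0.388 × 0.5 = 0.69.
- Sizes 4, 6 and 8 mixed: 67.9% overall, from 63.7% unequal and 78.1% right when unequal.

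**Two counselors who do not share information** (each assignment seen with probability one half): about 53–54% correct for fixed blocks of 4, fixed blocks of 6, or the two mixed.

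**The case against.** The case on the other side has real weight.

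- **Knowledge of past assignments is inferred.** Section 15.1 refers to counselors in the plural and 15.2 plans comparisons between counselors. If a site has two who do not share information, prediction is close to chance. This stands, and the higher figures are conditional on one counselor per site or shared knowledge.
- **Block size is withheld.** The certainty counts do not apply unless the size is fixed and worked out, and the Lead Node may already vary it. This also stands. It does not remove guessing, which stays near 68–69% with mixed blocks for someone who sees every assignment.
- **The order of steps is set.** The heading of section 10.0, section 9.1 and the sequence in 10.3.2 all put the review before the envelope. A reader might infer that the envelope may be opened first; the text does not allow that. Anticipating the arm is a different matter and is not prevented.
- **Discretion is limited.** Review depth is meant to depend on what the residential counselor did, timing is anchored to planned discharge, and the research assistant confirms eligibility. What remains is chiefly the order of participants discharged close together, and how often that occurs cannot be computed from the Protocol.
- **The review may do little.** Section 4.1 cites a study in which pre-discharge aftercare orientation did not significantly change attendance. That weakens the review-depth channel but does not touch the order channel, which acts through who enters which arm.
- **The efficacy analysis is exploratory.** Section 13.3.1 sets no significance level and warns against definitive conclusions. Urine and breath tests, and verification of attendance where feasible, supplement self-report. This limits the consequence, though the effect size is still meant to be carried forward.

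The Counselors Manual, to which 10.3.2 refers for detail, is not shown and may add safeguards.

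**Conclusion.** The point holds as a weakness of allocation procedure. The call-giving counselor takes the next envelope from a site-stratified blocked sequence, timing is flexible and no envelope is committed to a participant in advance. With one counselor per site or shared knowledge, about 64–75% of assignments could be guessed (blocks of 12 down to 2). About 14–50% would be certain if the block size is fixed and known or inferred. With two counselors who do not share information, guessing is about 53–54%.

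These figures measure predictability, not bias. They show an opportunity for envelope order, and to a lesser degree review depth, to follow the expected arm. What is exposed is the exploratory effect size (5.1 item 7, 13.3.1).

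A reader might go further and infer that upcoming assignments are generally known, that the comparison is therefore biased, or that the feasibility results are compromised. The Protocol supports none of these. Many assignments stay unpredictable under any block size, no shift in an outcome can be derived from the text, and most feasibility proportions, such as consent and call delivery, do not depend on which arm a participant enters.

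**What to change.** In 10.3.2 and 11.5:

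1. When eligibility is confirmed at the pre-discharge interview, before the counselor meeting, the research assistant writes the participant number, date and time on the next sealed envelope.
2. The counselor opens only that envelope, and only after recording that the plan review is complete and whether it was a full review or a comprehension check.
3. The counselor, not the research assistant, enters the arm, kept apart from the part of the Randomization Form that the assistant reviews, so that the week-13 assessor need not learn it from there.
4. If the Lead Node does not already do so, it uses varying block sizes that are not disclosed to sites.

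Labelling is the effective step: it takes the envelope order out of the counselor's hands. Recording the review only limits and documents the depth channel, since the counselor still knows past arms. Varying blocks remove certainty about a known size but leave most of the guessing.

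The cost is wording in two sections and a short record line, with existing staff and envelopes. The downside is that an envelope labelled for someone who leaves before randomization must be returned unopened and logged, leaving a few gaps in the sequence.
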